14.3 Secondary Objectives

The secondary objective of this study is to determine the antibody response of both vaccines and their combination as measured by ELISA and transmission-blocking assays as measured by SMFA and DSF and the effect on antibody responses of a third dose.

Anti-Pfs25 antibody will be measured by ELISA on vaccination days, 2 weeks after each vaccination, and periodically until study completion. Antibody responses over time will be shown graphically with geometric mean antibodies and the associated confidence intervals based on the t-distribution applied to the log-transformed responses. The smaller (n=5 and n=10) groups are primarily included for safety, and their ELISA response will only be used in an exploratory nature. They will not be included in the main analysis of the secondary endpoint. We will compare antibody and functional assay responses within Arms over time.

We will also look at differences in antibody decline over time in the vaccination groups.

Graphs will display transmission-blocking assays as a function of ELISA antibody levels.

Preliminary results for the SMFA and ELISA have been ascertained for Day 252 (12 weeks post-dose 3). They have been discussed with the scientific advisory board (SAB) and the data safety monitoring board (DSMB). The conclusion to combine groups for the full booster dose was based on the facts that fractional (1/5 the amount of antigen and adjuvant) dosing (marginally) failed ($p=0.0597$) to be statistically significantly different than full dosing when looking at TRA readouts from the SMFA while being statistically significantly different in ELISA titer readouts

($p=0.00014$). The combined group will be given the full dose in an effort to maximize power to detect a signal. The unblinding occurred as originally planned, with some of the members of the clinical team unblinded later than others as they completed database clean up procedures. Some of the lab teams are still blinded as they are still performing assays. They will be unblinded once these tasks are completed. The DSMB has always received unblinded information throughout the study. The study is being extended for one year in order to assess the kinetics of the fs230 antibody titers with (main phase) and without (pilot phase) a booster vaccination in the second transmission season. The possibility for an enrollment differential between the study arms in the study extension does exist, but is not anticipated due to re-enrollment being very successful in a previous study in this area. The loss to follow-up thus far has not appreciably been affecting one group more than another.

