A total of 305 subjects will be enrolled at multiple sites in Mali, West Africa to receive escalating doses of a malaria transmission blocking vaccine (s): Pfs25M-EPA/AS01, Pfs230D1M-EPA/AS01, or simultaneous administration of Pfs25M-EPA/AS01 and Pfs230D1M-EPA/AS01; or a comparator vaccine (ENGERIX-B). Enrollment within each group will be staggered for additional safety and subjects will only be enrolled into the co-administration group once each individual dose has been administered. Subjects will be followed for at least 6 months after the last vaccination. Safety outcomes will be local and systemic adverse events and serious adverse events. Immunogenicity outcomes will be antibody responses as measured by ELISA against recombinant Pfs25, Pfs230, EPA, CSP, and B cell and T cell responses. Functional activity of the induced antibodies will be assessed in TBV arms by standard membrane feeding assays conducted at the National Institute of Allergy and Infectious Diseases, and activity that interrupts malaria transmission will be measured in the double-blind portion of the study by direct skin feeding assays in Mali.

Subjects in the open label safety cohorts (Arms 1a, 1b, 2a, 2b, 3a, 3b, 4a, 4b) will be offered re-enrollment for follow-up laboratory assessment to explore the duration of immunogenicity and functional activity at approximately 9, 12 months post vaccination. Following scheduled, intentional unblinding, subjects enrolled in Arms 2c, 2d, and 4c will be provided the opportunity to re-enroll for a fourth vaccination (Arm 2c and 2d with 40 µg dose of Pfs230D1M-EPA/AS01; Arm 4c with Menactra[®]) approximately 1 year post vaccination #3. Subjects in these arms will also be eligible to re-enroll for follow up of duration of immunogenicity and functional activity at approximately 9, 12 months post vaccination if they choose not to enroll to receive the booster vaccination. Subjects will be followed similarly to the previous year for safety, immunogenicity, and functional activity.

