3.1.2 Pfs25H-EPA/Alhydrogel® in Healthy Malian Adults

A double-blind dose-escalating randomized controlled phase 1 study in malaria exposed adults of the safety and immunogenicity of Pfs25H-EPA/Alhydrogel[®] was conducted in Bancoumana, Mali. One hundred twenty subjects were enrolled and randomized to receive the low dose (16µg of conjugated Pfs25, n=10), the high dose (47µg of conjugated Pfs25, n=50), or the comparator vaccine (Euvax B for first 3 vaccinations, then Menactra[®] for the fourth vaccination, n=10 for 2 vaccinations, n=50 for 4 vaccinations) (Figure 8). Enrollment within the high dose group was staggered for additional safety. The low dose and the matching comparator cohort (Group 1) received 2 vaccine doses given at 0 and 2 months. For the rest of the subjects, 3 doses were given at a 0, 2, 4 month dosing intervals in 2013, and a fourth (booster) dose at 12 months after the third dose at the start of the subsequent transmission season in 2014. Subjects were followed for at least 6 months following the last vaccination. In total, 82 subjects (40 comparator cohort and 42 Pfs25 high dose cohort) received their fourth vaccination.

Figure 8: Phase 1 Study of Pfs25H-EPA Conjugates in Malian Healthy Adults

Arrows indicate timing of vaccinations. Direct skin feeds (DSF) in 2013 completed only on gametocyte or parasite carriers. DSF in 2014, following receipt of vaccination #4, completed weekly on all eligible subjects starting 2 weeks post dose #4 and continuing for 6 consecutive weeks.

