3.1.4 Pfs25M-EPA/Alhydrogel[®] in Healthy Malian Adults

The phase 1 study of the safety and immunogenicity of Pfs230D1M-EPA/Alhydrogel[®] and Pfs25M-EPA/Alhydrogel[®] (NIAID protocol #15-I-0044) started in April 2015 in Mali and has completed enrollment ([Table 5](#)).

Cohort 1, which included the single antigen safety Arms A1 (Pfs25M, 16 μ g), B1 (Pfs230D1M, 15 μ g), and D1 (Twinrix[®]), and Cohort 2, which included the co-administration safety Arm C1 (Pfs25M, 16 μ g + Pfs230D1M, 15 μ g) and D2 (Twinrix[®] + normal saline) have completed enrollment, all vaccinations (2 of 2 scheduled at 0, 1 month intervals), and undergone scheduled unblinding per protocol in October 2015.

Cohort 3, which includes increased sample size for immunogenicity and functional activity assessment, included Arms A2 (Pfs25M, 47µg + normal saline), B2 (Pfs230D1M, 40µg + normal saline), C2 (Pfs25M, 47µg + Pfs230D1M, 40µg) and D3 (Twinrix® + normal saline) have completed enrollment, 3 of the 4 scheduled vaccinations (0, 1, 6 months), and undergone 6 weeks of intensive twice a week DSF assessment. Subjects in cohort 3 who are currently active on protocol (171 of 200) are in long term safety follow-up and will receive Vaccination #4 in September 2016, undergo evaluation via DSF following receipt of Vaccination #4, and be unblinded in March/April 2017.

Table 5: Subject Enrollment and Vaccination in Mali

Arm	Dose	Enrolled	Received Vaccination #1 (D0)	Received Vaccination #2 (D28)	Received Vaccination #3 (D168)	Completed Final Study Visit/ On Protocol
Cohort 1 - unblinded						
A1	Pfs25M, 16µg	5	5	5	N/A	5
B1	Pfs230D1M, 15µg	5	5	4	N/A	4
D1	Twinrix®	5	5	5	N/A	4
Cohort 2 - unblinded						
C1	Pfs25M, 16µg + Pfs230D1M, 15µg	5	5	5	N/A	5
D2	Twinrix® + NS	5	5	5	N/A	4
Cohort 3 - blinded						
A2	Pfs25M, 47µg + NS	200	200	190	177	171
B2	Pfs230D1M 40µg + NS					
C2	Pfs25M, 47µg + Pfs230D1M, 40µg					
D3	Twinrix® + NS, then Menactra + NS					

NS = normal saline. N/A = not applicable.

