5.1.2 Bancoumana and Doneguebougou Main Study

The double-blind, randomized, comparator controlled portion of the study is designed to also evaluate study vaccine safety and reactogenicity in healthy malaria-exposed individuals, but is powered as well to assess for immunogenicity and functional activity via SMFA and DSF.

Following scheduled, intentional unblinding at study day 336, subjects from the main study will be offered re-enrollment into the open label fourth vaccination.

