12.13 Unblinding

Intentional, unscheduled unblinding may occur if a subject experiences a SAE that the treating clinician and/or site PI believes warrants unblinding to provide appropriate clinical management of the subject. The request for unblinding may be requested by the site PI or designee, Sponsor, Sponsor Medical Monitor, Independent Medical Monitor, and Data Safety Monitoring Board (DSMB). If non-emergent, all parties should be notified to discuss prior to unblinding taking place. If unblinding is requested, an “Unblinding Report” should be documented per standard operating procedures and submitted to the study statistician for formal unblinding.

If emergency unblinding is required, the PI or designee will contact the study statistician or study pharmacist for unblinding. The Sponsor will be informed within 1 business day that the unblinding was necessary and a submitted “Unblinding Report” will be provided within 2 business days.

Subjects who are unblinded will be encouraged to remain in the study to be followed for safety.

After the time of unblinding, subjects in the experimental vaccine cohort will be offered vaccination with ENGERIX-B, or another FDA-approved Hepatitis B containing vaccine, according to the usual, FDA approved schedule.

Scheduled unblinding for Arms 2c, 2d, 4c will occur on Study Day 336 as already outlined in [Appendix B](#) and [C](#). Scheduled unblinding will be reported to the DSMB at the time of the next meeting.

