14.6 Randomization

See [Section 8.2](#) for more information.

Enrollment into the Bamako/Sotuba, Mali portion of the study will be randomized as follows:

- Arms 1a and 2a will be enrolled 1-1 with random block based on time of enrollment/randomization;
- Arm 3a will not have a concurrent arm, so there will be no randomization for that arm;
- Arms 1b, 2b and 4a will be enrolled 1-1-1 with the same style of random block based on time of enrollment/ randomization;
- Arms 3b and 4b will be enrolled 1-1 with random block based on time of enrollment/randomization.

Enrollment into the Bancoumana/Doneguebougou, Mali portion of the study will be randomized in random blocks of size no greater than 8 and stratified by village. In order to accomplish this, a list of all enrolled subjects will be given to the study statistician for the first randomization. As subjects that dropout after randomization, and are not vaccinated, cannot be replaced, randomization and first vaccination should occur as close in time as possible to avoid having subjects in the ITT efficacy and safety analyses that have never received vaccination or comparator. Randomization lists are not produced pre-enrollment to reduce the risk of on-site operational error in randomization assignment, which given the stratified nature of the randomization would require management of several lists.

Randomization will occur **between arms** as follows in the Bancoumana/Doneguebougou study:

- Arms 2c, 2d, and 4c will be enrolled 1-1-2 with random block sizes no greater than 8.

Randomization between the arms allows for causal comparisons of ELISA and functional assay responses.

15 Human Subject Protections and Ethical Obligations

This research will be conducted in compliance with the protocol, Good Clinical Practices (GCP), and all applicable regulatory requirements.

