3. Record AEs and concomitant medications, if applicable.
4. Obtain approximately 7 mL of blood for malaria blood smear, malaria PCR, SMFA, and anti-Pfs230 antibody ELISA.

Study Day 308 (±21 days; 140 days after Vaccination #3)

1. Perform basic history and focused physical examination, emphasizing examination of any acute complaints.
2. Record vital signs (blood pressure, temperature, and heart rate).
3. Record AEs and concomitant medications, if applicable.
4. Obtain approximately 1 mL of blood for malaria blood smear and malaria PCR.

Study Day 336 (±21 days; 168 days after Vaccination #3)

1. Perform basic history and focused physical examination, emphasizing examination of any acute complaints.

2. Record vital signs (blood pressure, temperature, and heart rate).
3. Record AEs and concomitant medications, if applicable.
4. Obtain approximately 47 mL of blood for malaria blood smear, malaria PCR, SMFA, and anti-Pfs230 antibody ELISA, and cellular assays, *ex vivo* assays, B cell assays and transcriptional analysis.
5. Scheduled unblinding of all subjects
 - a. Offer ENGERIX-B (or other approved Hepatitis B vaccine) to those subjects that received TBV(s) during the study.

Re-enrollment visits

Study Day 462 +/-70 days (294 days after Vaccination #3); Re-screening

1. Explain the study and informed consent document to the subject.
2. Ensure the subject has acknowledged consent by signing or fingerprinting the informed consent document. Ensure that the subject receives a signed copy of the informed consent.
3. Elicit a complete medical history, including menstrual and contraceptive history and/or history of surgical sterility for females, and medication use.
4. Females of childbearing potential must be willing to use reliable contraception from at least 21 days prior to fourth vaccination through three months after the fourth vaccination.
5. Administer a complete physical examination, including vital signs (height, weight, blood pressure, temperature, and heart rate).
6. HIV pre- and post-test counseling as indicated including follow-up contact with subject to report the results and referral for appropriate medical care if indicated.
7. Obtain approximately 16 mL of blood for complete blood count (CBC) with differential and platelet count, ALT, creatinine (Cr), hepatitis B surface antigen, hepatitis C antibody, HIV antibody, malaria blood smear, malaria PCR, SMFA, and anti-Pfs230 antibody ELISA.

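### The dose-4 skin-feed comparison is among subjects who choose to re-enrol after learning their arm, yet the plan neither limits its causal claim nor attaches any check for this

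*Combined protocol and SAP*

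**What the plan says.** The sequence is explicit. Section 12.13: "Scheduled unblinding for Arms 2c, 2d, 4c will occur on Study Day 336". The Précis: "Following scheduled, intentional unblinding, subjects enrolled in Arms 2c, 2d, and 4c will be provided the opportunity to re-enroll for a fourth vaccination". Section 5.1.2 makes the booster phase open label: "subjects from the main study will be offered re-enrollment into the open label fourth vaccination". Appendix C dates the new consent: "Study Day 462 +/-70 days (294 days after Vaccination #3); Re-screening". Subjects who decline the booster may take duration follow-up only (Précis).

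Section 14.5 (DSF) makes combined Arms 2c and 2d against controls the primary endpoint for the booster, analysed with a binomial GEE for which no covariates are named. Section 14.3 concedes that re-enrolment could differ between arms but does not expect it, "due to re-enrollment being very successful in a previous study in this area". It adds that losses so far have been similar across groups, with no numbers. Section 14.6 states: "Randomization between the arms allows for causal comparisons of ELISA and functional assay responses". Section 14 defines no booster analysis set, no comparison of re-enrolled with other subjects, and no adjustment or sensitivity analysis for re-enrolment.

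**The concern.** Randomisation made the three arms comparable at Day 0. The dose-4 comparison uses only those who later consent again, and they do so knowing their arm. The offers differ: another investigational dose in 2c and 2d, a licensed meningococcal vaccine in 4c. If people prone to carrying and transmitting parasites accept at different rates in different arms, the arms differ in infectiousness before dose 4 has any effect.

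Few subjects drive the DSF result. In #15-I-0044 after dose 3, 6 of 43 comparators gave all 18 positive comparator feeds; after dose 4, 4 of 39 gave 4 (Table 7). The balance seen so far cannot settle the matter, because the choice in question is made only after unblinding.

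**Working it through.** **1. Order of events.** The Day 336 visit has a ±21-day window, so it ends by Day 357. Re-screening opens at 462 − 70 = Day 392, which is 35 days later. Section 8.1.2 names Day 364 for the re-screening laboratory tests, also after Day 357. Consent follows unblinding on either date.

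**2. What the described precedents show.** Section 3 describes two earlier Malian trials with a fourth dose.

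- #15-I-0044 (Section 3.1.4): Cohort 3 subjects "will receive Vaccination #4 in September 2016, undergo evaluation via DSF following receipt of Vaccination #4, and be unblinded in March/April 2017". Dose 4 was therefore given under blind.
- #13-I-N109 (Section 3.1.2): double-blind, with no unblinding date given; "82 subjects (40 comparator cohort and 42 Pfs25 high dose cohort) received their fourth vaccination". From dose 3 to dose 4 (Table 2B), vaccine 42/45 = 93% and comparator 40/42 = 95%.
- #15-I-0044, participation around dose 4: 171 subjects were on protocol beforehand, and 158 (Table 7) or 160 (text) then had at least one DSF, which is 92% to 94%.

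Neither trial is described as offering re-enrolment to subjects who knew their arm.

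**3. The plan's power figure.** Inputs from Section 14.5 are control infectivity 14.8%, vaccine effect 80% and 120 × 0.9 = 108 in 2c+2d. I took 108 controls likewise, and two-sided 0.05 (stated for ELISA, assumed here). The vaccine-arm risk is 0.148 × 0.20 = 0.0296. A two-proportion normal approximation gives 86.9% and Fisher's exact test 85.1%, against the stated figure of about 85%. This is a subject-level check; the GEE cannot be rerun because no within-subject correlation is given.

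**4. Loss of numbers alone.** With the same inputs, 82% retention in both arms (98 each) gives 83.5%. With vaccine uptake at 90% and control uptake at 80%, 70% or 60%, power is 85.2%, 83.2% or 80.7%. Unequal numbers cost little; the exposure is bias.

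**5. Selection on a risk marker (assumed).** Suppose 36% of subjects carry nearly all the risk. The figure is borrowed from 14/39 gametocytaemic comparators after dose 4 in Table 7; the documents do not establish the link. If these subjects re-enrol at rate h and the rest at rate l, their share among re-enrollers is 0.36h / (0.36h + 0.64l), and the arm's risk changes by that share divided by 0.36.

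| h | l | Share | Risk factor |
|---|---|---|---|
| 0.75 | 0.85 | 0.332 | 0.92 |
| 0.65 | 0.85 | 0.301 | 0.84 |
| 0.85 | 0.75 | 0.389 | 1.08 |
| 0.85 | 0.65 | 0.424 | 1.18 |

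If this happens in the vaccine arms only, the apparent effect is 1 − (1 − true effect) × factor:

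| True effect | Factor 0.84 | Factor 1.18 |
|---|---|---|
| 80% | 83% | 76% |
| 50% | 58% | 41% |
| 30% | 41% | 17% |
| 0% | 16% | −18% |

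**6. Selection on infectiousness itself (assumed).** Take no vaccine effect, 90% re-enrolment in both arms and selection in the vaccine arms only. If would-be infective vaccinees re-enrol at r times the others' rate, the observed risk is 0.148r / (0.148r + 0.852).

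| r | Observed risk | Spurious effect | Chance of significance favouring vaccine (nominal 2.5%) |
|---|---|---|---|
| 0.90 | 0.135 | 9% | 4.5% |
| 0.75 | 0.115 | 22% | 10.6% |
| 0.50 | 0.080 | 46% | 34.9% |

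The documents give no value for r.

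**The case against.** The strongest reply is that nothing suggests the selection would be informative by arm. Feeds and compensation are the same in all main arms (Table 17). Menactra is also offered to TBV subjects who take dose 4 (Section 7.2.2), and hepatitis B vaccine to TBV subjects (Sections 7.2.1 and 12.13). Year-1 smear positivity and clinical malaria did not differ between arms (Section 3.5.2.2, all p ≥ 0.60). Of the 240 in the main study, 236 can be approached for re-consent. Section 14.3 discloses the possibility, and Section 14.1 calls the study exploratory. The causal sentence sits in the randomisation section and may have been meant only for the original allocation. All of this stands: it lowers the likelihood and size of a bias. It does not supply a check, and the sentence as written carries no limit.

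A reader might also infer that the plan relies on precedents that were all blinded. The documents do not support that. Section 14.3 cites one unnamed study, and dose 4 under blind is documented only for #15-I-0044.

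Nor do the precedents show poor uptake. Dividing 82 by 100, or 158 to 160 by 200, gives 79% to 82%, but this counts losses before dose 3, and the #15-I-0044 count is of subjects with a DSF rather than subjects boosted. The step that matters, dose 3 to dose 4, was well retained.

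**Conclusion.** The point holds in limited form. The dose-4 DSF comparison is among people who re-enrol knowing their arm, so randomisation protects it only in part. The plan's reassurance gives no study name or figure, and the one fourth-dose precedent with documented timing did not test a choice made after unblinding.

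The size is conditional on assumed selection rates. Under the marker assumption the bias is small against the 80% effect the trial is powered for, but comparable with a null or partial effect. Section 14.5 itself allows for a leaky vaccine, so a partial effect is a realistic case. About 18 infective controls are expected among 120 (0.148 × 120 = 17.8), which is why modest selection can show.

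Two stronger readings are not supported. The first is that a differential has occurred or that the comparison is invalid: none has been shown. The second is that the booster ELISA results fall too. The three key booster ELISA questions in Section 14.5 compare dose 4 with earlier doses, not arm with arm. The arm-against-control ELISA contrasts after dose 4 do share the selection, but each vaccine arm already differed from control at p<0.0001 twelve weeks after dose 3 (Figure 20), so selection is unlikely to reverse them.

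**What to change.** 1. In Sections 14.3 and 14.6, limit the causal statement to comparisons before unblinding, and describe the dose-4 arm comparison as one among re-enrollers.
2. Report re-enrolled against not re-enrolled by arm, with all 240 randomised as the denominator, on village, age, and Year-1 smear parasitaemia and gametocytaemia.
3. Add village (the randomisation stratum) and Year-1 smear parasitaemia to the dose-4 DSF GEE, and keep the unadjusted result alongside. Smear parasitaemia is measured after randomisation, but the vaccine is not designed to change it and Year-1 smear positivity was similar across arms. Do not adjust for the Year-1 DSF result, which the vaccine may have altered.
4. Use any inverse-probability-of-re-enrolment weighting as a sensitivity analysis only; with so few infective subjects the weighted estimate could be unstable.

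The cost is some wording, one table and one or two model terms, all on data already collected. The downside is those extra terms with sparse events, which is why the unadjusted result should stay.

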14.4 Exploratory Objectives

We will characterize and compare host immune responses, proteomic profiles, co-infection status, antibody repertoires, and transcriptomes to malarial antigens and to vaccine antigens in African adults prior and after immunization with Pfs230D1M-EPA/AS01 by mixed effects model or Wilcoxon signed rank test depending on the type of immune response. We will also make figures depicting immune response based on the study arm.

We will explore the impact of Pfs230D1M-EPA/AS01 on the genotype and transcriptome profile of parasites isolated from study subjects via standard regression analysis.

Should the study be terminated early, the investigative team will discuss with the DSMB the reason for termination and determine which study questions can be addressed in an unbiased manner with the available data. The available data will be analyzed and interpreted in light of early termination.

